4.2 Eligibility Criteria for the Treatment-naive Open-label Arm

4.2.1 Inclusion Criteria for the Treatment-naive Open-label Arm

- 1. Pathologically confirmed treatment-naive MCL (tumor tissue), with documentation of either overexpression of cyclin D1 in association with other relevant markers (eg, CD19, CD20, PAX5, CD5) or evidence of t(11;14), as assessed by cytogenetics, fluorescent in situ hybridization (FISH), or polymerase chain reaction (PCR)
 - A report from the local laboratory is acceptable if available; however, it must be reviewed and approved by the central pathology laboratory to verify the above criteria prior to enrollment
 - If the report from the local laboratory is not available, a tumor block or slides must be sent to the central pathology laboratory for confirmation of the MCL diagnosis prior to enrollment
- 2. Men and women ≥ 18 years of age with a TP53 mutation⁴
- 3. At least 1 measurable site of disease that is \geq 2.0 cm in the longest diameter and measurable in 2 perpendicular dimensions per CT
- 4. Subjects must have adequate fresh or paraffin-embedded tissue
- 5. Eastern Cooperative Oncology Group (ECOG) performance status (PS) of ≤ 2
- 6. Adequate hematologic function independent of transfusion and growth factor support for at least 7 days prior to first dose, with the exception of pegylated G-CSF (pegfilgrastim) and darbepoeitin which require at least 14 days prior to the first dose defined as:
 - Absolute neutrophil count (ANC) $> 1000 \text{ cells/mm}^3 (1.0 \text{ x } 10^9/\text{L})$

⁴ TP53 test by local or central lab

- Platelet count $> 50,000 \text{ cells/mm}^3 (50 \text{ x } 10^9/\text{L})$
- Hemoglobin > 8.0 g/dL
- 7. Adequate hepatic and renal function defined as:
 - Serum aspartate transaminase (AST) or alanine transaminase (ALT) ≤ 3.0 x upper limit of normal (ULN)
 - Estimated Creatinine Clearance (CrCl) ≥ 30 mL/min (Cockcroft-Gault)
 - Bilirubin ≤ 1.5 x ULN (unless bilirubin rise is due to Gilbert's syndrome or of non-hepatic origin)
- 8. Prothrombin time (PT) or International normal ratio (INR) < 1.5 x upper limit of normal (ULN) and PTT (activated partial thromboplastin time [aPTT]) < 1.5 x ULN (unless abnormalities are unrelated to coagulopathy or bleeding disorder). When treated with warfarin or other vitamin K antagonists, then INR ≤ 3.0
- 9. Male and female subjects of reproductive potential who agree to use both a highly effective method of birth control (eg, implants, injectables, combined oral contraceptives, some intrauterine devices [IUDs], complete abstinence⁵, or sterilized partner) and a barrier method (eg, condoms, cervical ring, sponge, etc) during the period of therapy and for 90 days after the last dose of study drug

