
that CR rates for MCL with a TP53 mutation are below the CR rates around 50% reported for BR in treatment-naive MCL. In the AIM study (Tam 2018), the CR rate for subjects with TP53 aberrations (mutations and deletions, n=12) is 50%; in the PHILEMON study, where R/R MCL patients received a combination of ibrutinib, rituximab and lenalidomide, similar proportions of patients with and without a TP53 mutation had an overall response and CR; when correcting for other prognostic factors, no PFS difference was seen between patients with and without a TP53 mutation (Jerkeman 2018). These encouraging data support the use of ibrutinib and venetoclax in patients with a TP53 mutation.

The randomized portion for R/R MCL has a PFS endpoint. For treatment-naive MCL, the endpoint of CR rate was chosen, also considering the small sample size (n=75). Durable CRs may represent clinical benefit and can be assessed earlier (compared to PFS).

In summary, exploring the combination of ibrutinib and venetoclax in treatment-naive MCL patients with or without a TP53 mutation is of interest with the goal to explore CR rates and other efficacy and safety parameters that can be achieved with this combination in comparison with historical CR rates and efficacy and safety data.

The R/R MCL population in this study is inclusive of MCL patients with blastoid variant; blastoid variant and MCL with a TP53 mutation are considered high-risk MCL populations. Since favorable outcomes in younger/fit/transplant-eligible patients with blastoid variant were observed with high-dose chemotherapy, high-dose consolidation and stem cell transplant (Dreyling 2018), contrasting young/fit/transplant-eligible patients with TP53 mutations who do not benefit from intensive chemotherapy and often relapse early (Eskelund 2017, Delfau-Larue 2015), MCL patients with blastoid variant are excluded from the open-label treatment-naive arm, and the focus is on the population with a TP53 mutation as the high-risk group for treatment-naive subjects.

1.4.8 Sample Size Considerations for Treatment-naive Open-label Arm Including **Patients with a TP53 Mutation**

A sample size of 75 treatment-naive subjects is needed to exclude a 35% CR rate at a 1-sided significance level of 0.025 with approximately 80% power, assuming a target CR rate of 51%.

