For the subpopulation with a TP53 mutation, a sample size of 48 subjects is needed to exclude a 25% CR rate with approximately 80% power, assuming a target CR rate of 45%. The TP53 population could be a mix of treatment-naive MCL subjects and/or R/R MCL subjects with a TP53 mutation.

Based on a historical CR rate of approximately 50% with BR (Flinn 2014, Rummel 2005, Rummel 2014, Chen 2017, Rummel 2017) in transplant-ineligible treatment-naive MCL subjects, the success criteria were set at excluding a CR rate of 40% for the transplant-ineligible treatment-naive MCL patients ≥ 65 years. Since the CR rates for MCL patients with TP53 mutations are estimated to be lower (Eskelund 2017), the success criteria were set at excluding a 25% CR rate for the MCL patients with a TP53 mutation. In combination, for the entire cohort of 75 treatment-naive MCL patients, which contain at least one third of patients (n=25) with a TP53 mutation, the success criteria were set at excluding a 35% CR rate.

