3.1.3 Treatment-naive Open-label Arm

In the treatment-naive open-label arm, approximately 75 subjects will be enrolled and treated with ibrutinib 560 mg and venetoclax 400 mg. Among them, approximately 50 subjects ≥ 65 years and approximately 25 subjects with a TP53 mutation will be enrolled (Figure 9).

[figure not shown]
Figure 9. Study Design: Treatment-naive Open-label Arm

w/o = without; PD = progressive disease; WC = withdrawal of consent

Ibrutinib and venetoclax will be administered using the 5-week ramp-up schedule shown in Figure 10. Treatment-naive MCL patients will use the same dose and schedule as established in the Safety Run-in for the Randomization Phase of the study. Therefore, there will be no Safety Run-in for the treatment-naive cohort. *Note: Sponsor may hold enrollment for patients in the treatment-naive open-label arm to ensure that at least 25 patients with a TP53 mutation are enrolled.*

Figure 10. Venetoclax Standard Ramp-up Schedule

Subject eligibility will be determined up to 28 days prior to first dose of study treatment.

Subjects in the protocol-defined increased-risk for tumor lysis syndrome (TLS) group will be hospitalized for a minimum of 24 hours (and up to 48 hours at the discretion of the investigator) at the start of the 20 mg and 50 mg ramp-up dose of venetoclax for monitoring and prophylaxis of TLS; subjects in the low-risk for TLS group may be hospitalized at the discretion of the investigator.

Subjects will be treated with ibrutinib and venetoclax for approximately 104 weeks (2 years), followed by ibrutinib monotherapy until PD, unacceptable toxicity or withdrawal of consent or study closure. Venetoclax will be discontinued after 104 weeks (2 years) of treatment, regardless of response assessment.

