7.1.1.2 Confirm Eligibility

All necessary procedures and evaluations must be performed to document that the subject meets all of the inclusion criteria and none of the exclusion criteria until first dose of study drug (Section 4).

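### Treatment-naive inclusion criterion 2 admits only TP53-mutated subjects, which contradicts the planned make-up of the arm and the 35% CR bar set for it

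*Protocol*

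**What the plan says.** Protocol 4.2.1, criterion 2, reads "Men and women ≥ 18 years of age with a TP53 mutation". The synopsis words it identically. None of the nine criteria in 4.2.1 offers an age-65 route or mentions transplant ineligibility. Section 7.1.1.2 says: "All necessary procedures and evaluations must be performed to document that the subject meets all of the inclusion criteria".

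The design text describes a different population. Section 3.1.3 plans about 75 subjects, of whom "approximately 50 subjects ≥ 65 years and approximately 25 subjects with a TP53 mutation will be enrolled". The synopsis, Sections 3.1, 5.1.4 and 10, and SAP 1.1 give the same make-up. Section 1.4.7 says that exploring the combination in "treatment-naive MCL patients with or without a TP53 mutation is of interest".

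Section 1.4.8 sets three CR bars:
- for the older group, "the success criteria were set at excluding a CR rate of 40% for the transplant-ineligible treatment-naive MCL patients ≥ 65 years";
- for the mutated group, "the success criteria were set at excluding a 25% CR rate for the MCL patients with a TP53 mutation";
- for the whole arm, "the success criteria were set at excluding a 35% CR rate"; the arm is described there as one in which 25 of the 75 subjects, or more, carry the mutation.

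Section 10.4 sizes the arm at 75 to exclude 35% at 1-sided 0.025 with about 80% power if the true CR rate is 51%. It gives the TP53 population a 25% null and a 45% target.

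**The concern.** The entry criterion and the sample-size rationale describe different populations. A site following 4.2.1 exactly would turn away every unmutated subject, including the older patients whom Sections 1.4.7 and 1.4.8 plan for. An unmutated subject who did enter would be an eligibility deviation on the current text. The note in Section 3.1.3 that the sponsor may hold enrollment to secure at least 25 TP53 subjects serves no purpose if everyone must carry the mutation.

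The mismatch reaches the analysis because the 35% bar depends on the mix. It suits an arm with about one third TP53 subjects. For an arm made up entirely of TP53 subjects, Section 1.4.8 itself gives 25%.

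**Working it through.** **Inputs.** N = 75, null 35%, 1-sided alpha 0.025, target 51%, TP53 null 25% and TP53 target 45% (Section 10.4); group bars 40% and 25% (Section 1.4.8); mix 50:25 (Section 3.1.3). The rule is the smallest r with P(X ≥ r | N, p0) ≤ 0.025, exact binomial.

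**1. The plan's own figure.** For N = 75 and p0 = 0.35, r = 35.
- P(X ≥ 35 | 0.35) = 0.0245.
- P(X ≥ 35 | 0.51) = 0.807.
- The lower limit of the exact 95% CI at 35/75 is 35.05%, so the rule agrees with the interval specified in Section 10.5.2.1.

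The stated power of about 80% reproduces.

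**2. Where 35% comes from.** (50 × 40% + 25 × 25%)/75 = (20 + 6.25)/75 = 35.0%. The protocol does not print these weights beside the bar, so the derivation is an inference, but the match is exact.

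**3. Criterion 2 as written, all 75 mutated.** The same weighting gives (0 × 40% + 75 × 25%)/75 = 25%. At the 45% TP53 target:
- against 35% (r = 35), power = P(X ≥ 35 | 0.45) = 0.429;
- against 25% (r = 27, alpha 0.0223), power = P(X ≥ 27 | 0.45) = 0.955.

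**4. Intermediate mixes and the direction of the error.** The blended bar is (n₁ × 40% + n₂ × 25%)/75, with n₁ older and n₂ TP53 subjects. The last column assumes a 45% CR rate in TP53 subjects and 54% in the older group. The 54% is not in the documents; it is back-solved as (75 × 51% − 25 × 45%)/50. Power is the chance of at least 35 CRs from the sum of the two binomials.

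| Older : TP53 | Blended bar | P(X ≥ 35) at that rate | Power of the 35-CR rule |
|---|---|---|---|
| 50:25 | 35% | 0.0245 | 80.8% |
| 40:35 | 33% | 0.0095 | 74.5% |
| 30:45 | 31% | 0.0032 | 67.4% |
| 0:75 | 25% | 0.00004 | 42.9% |

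As the TP53 share rises, the fixed bar becomes stricter: the false-positive risk falls and power is lost.

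**5. If both routes are admitted at 50:25**, the bar stays at 35% and power at 80.7%. No sample-size figure changes.

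**The case against.** The strongest reply is that criterion 2 was narrowed late, to finish TP53 accrual after the older group filled. The enrollment-hold note fits this, and the SAP Introduction says the cohort has completed enrollment. It may be true, and some front pages are not available to this review. But the criterion carries no such qualification, the design sections still describe both groups without mentioning closure, and no visible text records the change. If this is the explanation, one sentence would settle the matter.

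Second, rewording now changes nobody's entry. That stands. The value lies in knowing which subjects were eligible by which route, which the pending SAP addendum needs.

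Third, age 65 or over does not exclude a mutation, so the 50-subject target does not by itself contradict criterion 2. That also stands. The contradiction comes from the separate 40% and 25% bars, the one-third TP53 share, the with-or-without aim and the hold note.

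Fourth, the arm is exploratory. Section 10.5.2.1 specifies an estimate with an exact CI, and the TP53 population already has its own 25% bar. This limits the stakes but does not reconcile the text.

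**Conclusion.** Criterion 2 is inconsistent with the design and sample-size text and must be reconciled with it. The sample-size arithmetic is correct for the population it assumes. The randomized comparison is unaffected.

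Four stronger readings are not supported:
- **That the arm has 43% power.** This needs all 75 subjects to be mutated and a true CR rate of 45%. SAP 1.1 still describes a mix of about 50 and 25, and the hold note presupposes unmutated entrants. The figure is what the criterion implies if followed literally, not what the trial should expect.
- **That false positives are inflated.** The criterion pushes the TP53 share up, which makes the 35% bar conservative. Inflation would need a share below the one-third floor in Section 1.4.8. For example, an assumed 60:15 mix with each group at its own bar gives 5.3%; nothing in the documents indicates such a mix.
- **That the null should be reset to the enrolled mix.** In an open-label cohort that has finished enrolling, this would move a prespecified bar when responses may already be known. The documents also give no rule for weighting a subject who is both 65 or over and mutated.
- **That the protocol describes unmutated, transplant-ineligible subjects as two thirds of the arm.** Section 1.4.7 gives no proportions, and Section 3.1.3 specifies the older group by age alone. Transplant ineligibility appears only in 1.4.7 and 1.4.8.

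**What to change.** 1. Reconcile criterion 2 (Section 4.2.1 and the synopsis) with Sections 1.4.7, 1.4.8, 3.1, 3.1.3, 5.1.4 and 10. Either state both entry routes (the group aged 65 or over, with transplant ineligibility if intended as in 1.4.7 and 1.4.8; or age 18 or over with a TP53 mutation), or state that the criterion applied only to remaining TP53 accrual once the older group had closed, and from when.
2. Keep the prespecified 35% bar for the whole arm.
3. In the pending SAP addendum, report the enrolled mix and each subject's entry route. Give the CR rate with its exact CI in each group beside its existing bar: 40% for transplant-ineligible subjects aged 65 or over, 25% for TP53. State beforehand how subjects who belong to both groups are counted.

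The cost is a protocol clarification and a short paragraph in an addendum that is already due. There is no change to sample size and no new data collection, provided that age, mutation status and, if used, transplant eligibility were recorded at entry.

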4.2.2 Exclusion Criteria for the Treatment-naive Open-label Arm

- 1. Blastoid variant of MCL
- 2. History or current evidence of central nervous system lymphoma
- 3. Concurrent enrollment in another therapeutic investigational study or prior therapy, including ibrutinib or other BTK inhibitors
- 4. Prior treatment with venetoclax or other BCL2 inhibitors
- 5. History of other malignancies, except:
 - Malignancy treated with curative intent and with no known active disease present for ≥ 3 years before the first dose of study drug and felt to be at low risk for recurrence by treating physician
 - Adequately treated non-melanoma skin cancer or lentigo maligna without evidence of disease
 - Adequately treated carcinoma in situ without evidence of disease

About HMA/Working Groups/CTFG/2014 09 HMA CTFG Contraception.pdf

⁵ Complete abstinence is a highly effective method only if defined as refraining from heterosexual intercourse during the entire period of risk associated with the study treatments. The reliability of sexual abstinence needs to be evaluated in relation to the duration of the clinical trial and the preferred and usual lifestyle of the subject. http://www.hma.eu/fileadmin/dateien/Human Medicines/01

- 6. Vaccinated with live, attenuated vaccines within 4 weeks of the first dose of study drug
- 7. Clinically significant infection requiring IV systemic treatment that was completed ≤ 14 days before the first dose of study drug
- 8. Any uncontrolled active systemic infection
- 9. Known bleeding disorders (eg, von Willebrand's disease or hemophilia)
- 10. History of stroke or intracranial hemorrhage within 6 months prior to enrollment
- 11. Known history of human immunodeficiency virus (HIV) or active with hepatitis C virus (HCV) or hepatitis B virus (HBV). Subjects who are positive for hepatitis B core antibody, or hepatitis C antibody must have a negative polymerase chain reaction (PCR) result before enrollment. Those who are hepatitis B surface antigen (HBsAg) or PCR positive will be excluded.
- 12. Major surgery within 4 weeks of the first dose of study drug.
- 13. Any life-threatening illness, medical condition, or organ system dysfunction that, in the investigator's opinion, could compromise the subject's safety or put the study outcomes at undue risk
- 14. Currently active, clinically significant cardiovascular disease, such as uncontrolled arrhythmia or Class 3 or 4 congestive heart failure as defined by the New York Heart Association Functional Classification; or a history of myocardial infarction, unstable angina, or acute coronary syndrome within 6 months prior to randomization
- 15. Unable to swallow capsules or tablets, or malabsorption syndrome, disease significantly affecting gastrointestinal function, or resection of the stomach or small bowel, symptomatic inflammatory bowel disease or ulcerative colitis, or partial or complete bowel obstruction
- 16. Treatment with any of the following within 7 days prior to the first dose of study drug:
 - Moderate or strong cytochrome P450 3A (CYP3A) inhibitors (Appendix D)
 - Moderate or strong CYP3A inducers (Appendix D)
- 17. Administration or consumption of any of the following within 3 days prior to the first dose of study drug:
 - grapefruit or grapefruit products
 - Seville oranges (including marmalade containing Seville oranges)
 - star fruit
- 18. Known allergy to xanthine oxidase inhibitors and/or rasburicase for subjects with known risk factors (as defined by high tumor burden and/or diminished renal function, as detailed in "Study Design" section above) for TLS
- 19. Subjects with chronic liver disease with hepatic impairment Child-Pugh class B or C
- 20. Female subject who is pregnant, breastfeeding or is considering becoming pregnant during the study or for approximately 90 days after the last dose of study drug

- FINAL
- 21. Male subject who is considering fathering a child or donating sperm during the study or for approximately 90 days after the last dose of study drug
- 22. Unwilling or unable to participate in all required study evaluations and procedures
- 23. Unable to understand the purpose and risks of the study and to provide a signed and dated informed consent form (ICF) and authorization to use protected health information (in accordance with national and local subject privacy regulations)
- 24. Known hypersensitivity to the active ingredient or other components of one or more study drugs

5 TREATMENT OF SUBJECTS

5.1 Treatment Allocation and Blinding

5.1.1 Safety Run-in Period

Up to 27 subjects may be enrolled during the Safety Run-in Period. Initially, 6-9 subjects at low risk for TLS and 12 subjects at increased risk for TLS will receive ibrutinib at 560 mg once daily and open-label venetoclax at a starting dose of 20 mg once daily and gradually ramped up to a target dose of 400 mg once daily over a 5-week period. TLS events and DLT occurrence will be assessed during the venetoclax Ramp-up Period for a minimum of 5 weeks. Depending on the occurrence of TLS events and DLTs, a minimum of 6 additional subjects at increased risk for TLS may be treated with the 4-week ibrutinib lead-in during the Safety Run-in Period.

Subjects dosed in the Safety Run-in Period will continue on open-label ibrutinib at 560 mg once daily and open-label venetoclax at a target dose of 400 mg for up to approximately 104 weeks, followed by ibrutinib monotherapy until disease progression, unacceptable toxicity or withdrawal of consent.

5.1.2 Randomization Phase

The Randomization Phase portion of the study will follow a randomized, double-blind design. After written informed consent has been obtained and eligibility has been established, the study site will obtain the subject's identification number and treatment assignment from the Interactive Response Technology (IRT) System.

5.1.2.1 Randomization

Approximately 260 eligible subjects will be randomized at a 1:1 ratio to ibrutinib and venetoclax or ibrutinib and placebo treatment arms. Randomization will be stratified by number of prior lines of therapy $(1-2, \ge 3)$, ECOG PS (0-1, 2), and by TLS category (low risk, increased risk for TLS). Subjects will be dosed within 3 days of randomization.

Subjects will continue treatment with either ibrutinib and venetoclax or ibrutinib and placebo for at least 104 weeks, followed by ibrutinib monotherapy until PD, unacceptable toxicity or

withdrawal of consent. Venetoclax/placebo will be discontinued after 104 weeks of treatment, regardless of response assessment.

A stratified, permuted-block randomization will be implemented in order to obtain a balanced assignment to each treatment within levels of the stratification factors.

5.1.2.2 Blinding

Subjects, investigators, and the Sponsor's study team members will remain blinded to treatment assignment. The investigator will not be provided with randomization codes nor the treatment received. The codes will be maintained within the IRT System, which has the functionality to allow the investigator to break the blind for an individual subject if necessary to appropriately manage or treat the subject. Data that may potentially unblind the treatment assignment (ie, study drug plasma concentrations) will be handled with special care to ensure that the integrity of the blind is maintained and the potential for bias is minimized.

Telephone contact with the Sponsor or its designee will be available 24 hours per day, 7 days per week. In the event the blind is broken, the Sponsor must be informed as soon as possible. The date and time of the unblinding must be documented within the IRT System, in the appropriate section of the eCRF and in the source document. The confirmation received from the IRT System indicating the code break must be retained with the subject's source documents in a secure manner. A subject whose treatment assignment has been unblinded may continue the study treatment if the subject is expected to continue to receive clinical benefit. The subject should continue to return for scheduled study visits. The single-blind (ie, subject remains blinded to treatment assignment) should be maintained, provided the subject's safety is not compromised.

